3.2.1 Measure therapy response of patient specific uVESSEL model

Patient-derived uVESSEL models (from primary & metastatic sites) and incorporating patient-derived immune cells will be tested for response to anti-angiogenic therapies including pazopanib, sunitinib, cabozantinib, and axitinib. Response will be quantified via multiple endpoints, e.g. vessel sprouting, PSMA expression, cell death.

3.2.2 Evaluate the predictive power and validate the uVESSEL model

While a number of novel biomimetic approaches show promise in their ability to recapitulate physiologically relevant behavior, clinical validation is needed to determine if such approaches are predictive. Using the clinical, pathological and imaging endpoints under 3.1, we will develop predictive models using responses to uVESSEL model above. More specifically we will use the objective response (dichotomous endpoint of yes or no) measured using PSMA-based PET/CT as a dependent variable in a logistic regression model with response to uVESSEL model from above as an independent predictor to segregate uVESSEL responses into two groups corresponding to responders and non-responders to anti-angiogenic therapies.

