3.0 OBJECTIVES

3.1 Primary Objective: To evaluate response to systemic therapy, including anti-angiogenesis and/or immune-based therapies, via ¹⁸F-DCFPyL PSMA-based PET/CT in patients with metastatic renal cell carcinoma and to compare qualitatively with conventional imaging response criteria (RECIST 1.1) and other histopathological endpoints including isolation, enumeration and staining of Circulating Tumor Cells (CTC).

Response of systemic immune-based and/or anti-angiogenesis therapies will be quantified using PSMA-based PET imaging using a novel agent, ¹⁸F-DCFPyL, as a non-invasive imaging biomarker of tumor neovasculature to functionally monitor renal cell cancer neovasculature in patients undergoing systemic anti-angiogenesis therapy. PSMA PET will be compared with response to anti-angiogenesis therapy using conventional imaging computed tomography(CT)-based RECIST1.1 criteria (Eisenhauer 2009) as well as histopathological endpoints (tumor vascular density, immunohistochemical staining for PSMA and neovascularization (CD105, CD31). Whole body PSMA PET/CT scans will be obtained at baseline, following adjuvant anti-angiogenic therapy and when the patient becomes refractory to treatment.

The rationale and time points for obtaining PET scans is planned with respect to the typical natural history of metastatic RCC. This project will obtain information from tumors that are responding to anti-angiogenesis therapy and those resistant to treatment.

PET1 is obtained pre-surgically to establish the baseline tumor PET and CT characteristics prior to

surgical removal of the primary renal tumor and metastatic sites (e.g. LNs). Surgery technique is not altered for this study.

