Medical records will be reviewed to obtain medical history including physical exams, medications (all concomitant medications before and after each of the PET/CT scans, treatment medications for RCC), laboratory tests (metabolic chemistry, hematology, pathology), imaging results (all available CT, MRI, ultrasound, PET/CT) and information related to the diagnosing, treatment, or outcomes of the study subject's diagnosis, treatment and clinical follow-up up to two years from the time of initiation of systemic anti-angiogenesis therapy.

Remuneration

Subjects will receive \$50 per scan, for a total of up to \$300, as compensation for their participation in this study.

Withdrawal/Termination from Study

Reasons for withdrawal or termination

Enrolled patients will be removed from the study in the following circumstances:

- The patient does not complete the imaging examinations per study protocol
- The subject withdraws consent
- Exclusion criteria are discovered after registration but prior to the research examinations
- The PI or co-investigators determine it is within the best interest of the subject to remove them from the research.

Study Procedures Table

Study Procedures	Screening ¹	Baseline Prior to surgery	VISIT 2a and 2b Prior to and during 1 st systemic therapy	VISIT 3a and 3b Prior to and during 2 nd systemic therapy	VISIT 4 ²
Informed Consent ⁵	X				
Clinical History	X				
PET/CT Exam		X	X ⁴	X ⁴	X
Tissue Collection			X ³		

1. Screening visit may be completed on the same day as the baseline visit
2. To be done at the time of disease progression or within 2 years, whichever occurs first.
3. Tissue collection will occur post SOC surgery and will be coordinated with the UWCCC TSB.
4. PET/CT scan obtained prior to systemic therapy (immune-based and/or anti-angiogenesis therapy) and at 12-16 weeks into therapy
5. During the COVID-19 pandemic, consent procedures will be conducted by phone, when possible, to minimize face-to-face contact subjects have with the research team. An encrypted copy of the consent form will be mailed or emailed to subjects prior to the scheduled consent phone call.

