10.2 Statistical analysis

Statistical analysis will by necessity (n=15) and nature (predictive modeling of response using patient-derived ex-vivo uVESSEL responses as predictors, among others) be exploratory and descriptive including qualitative comparison between responses based on PSMA-PET and RECIST 1.1 without a formal paired test of statistical significance.

Measures of patient response to anti-angiogenics via clinical endpoint such as response based on PSMA-PET (primary endpoint) and objective response based on RECIST 1.1 and histopathological endpoints (tumor vascular density, immunohistochemical staining for PSMA and neovascularization (CD30, CD34)) will be summarized with descriptive statistics (response rate and confidence interval), and changes in these endpoints, PSMA staining from baseline to end of treatment and follow-up) will also be summarized with descriptive statistics. Measures of tumor neovascularization via PSMA-based PET/CT imaging will be summarized with descriptive statistics over time and analyzed using generalized linear mixed-effects models for longitudinal measures. Qualitative ¹⁸F-DCFPyL PSMA PET/CT imaging will be recorded in a three-point scale, and statistical analysis will be performed with the equivocal score of 1 considered as positive or negative. Histopathological endpoints will be qualitatively graded by our study pathologist on a zero to four scale with four being the highest level of immunohistochemical staining or neovascularization.

Partial responses are likely from conventional clinical imaging in mRCC patients. Standard imaging techniques define responses to therapy based on size changes of target lesions using RECIST1.1. Metastatic tumors may respond to anti-angiogenic treatment but not change substantially in size (unlike cytotoxic therapies for which RECIST was designed). To address this limitation in current imaging, we combine standard imaging with functional imaging protocols to evaluate whether angiogenesis decreases in individual metastatic lesions regardless of changes in tumor size. PSMA PET signal is used as a surrogate for changes in tumor neovasculature. These functional imaging findings will be

confirmed pathologically by evaluating angiogenesis/ PSMA expression in tumor samples and patient models. Using this approach, we will evaluate functional anti-angiogenesis responses to therapies.

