For the uVESSEL models (secondary objective 1), generalized linear mixed-effects models for longitudinal measures taken four times will be used for various endpoints with treatment (control plus four anti-angiogenics), dose (three levels each replicated three times), and plate (primary vs metastatic crossed by normal vs tumor) as the main factors. This will allow evaluation of the effects of treatment and dose and the differences between primary and metastatic samples and between normal and tumor vessels. We will also include these two models as the main factor in a combined generalized linear mixed-effects model, which will allow direct comparison of the biomimetic and the organotypic models.

Predictive modeling (secondary objective 2) will thus include the actual tumor size change (in a typical waterfall plot) and the dichotomy of disease control vs no disease control in the predictive model for tumor response in addition to the dichotomy of responders vs. non-responders in functional studies.

Due to limited sample size (n=15) and because not all patients are treated with the same anti-angiogenic therapy, further reducing the sample size for each anti-angiogenic therapy, one cannot expect the predictive analysis to give a clear discrimination between responders and non-responders to anti-angiogenic therapies. As an alternative, we will also use clustering analysis based on k-means or Gaussian mixture models which are less sensitive to small sample sizes as in Pak (2015).

Using the clinical, pathological and imaging endpoints as dependent variables, we will develop predictive models using responses to the uVESSEL model as independent predictor variables. More specifically, we will use the objective response as a dichotomous endpoint as a dependent variable in a logistic regression model with response to the uVESSEL model as an independent predictor. This approach is equivalent to linear discriminant analysis. Although we expect about 70% of eligible patients will receive pazopanib and the rest sunitinib, we can still use the objective response as the dependent variable in logistic regression as both pazopanib and sunitinib are expected to give a similar response rate of around 30% in this patient population. In addition each patient sample will be subject to both agents in the uVESSEL model and provide response to be used as predictors in logistic regression modeling.

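### Tissue pathology is listed as an outcome of the uVESSEL predictive models, but the only scheduled tissue is taken at surgery and cannot show response to therapy that starts later

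*Combined protocol and SAP*

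**What the plan says.** The secondary objective on predictive power and validation (3.2.2) states: "Using the clinical, pathological and imaging endpoints under 3.1, we will develop predictive models using responses to uVESSEL model above". Section 10.2 fixes the roles: "Using the clinical, pathological and imaging endpoints as dependent variables, we will develop predictive models", with uVESSEL responses as the independent variables.

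Section 3.1 names the tissue measures as "histopathological endpoints (tumor vascular density, immunohistochemical staining for PSMA and neovascularization (CD105, CD31". (Section 10.2 gives CD30 and CD34 as the vascular markers instead. That is a separate discrepancy and does not affect this point.) Section 3.1 also counts "other histopathological endpoints including isolation, enumeration and staining of Circulating Tumor Cells (CTC" under the same label.

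Section 10.2 lists the histopathological endpoints in a sentence that opens "Measures of patient response to anti-angiogenics via clinical endpoint such as response based on PSMA-PET (primary endpoint", and adds a summary of how PSMA staining changes through treatment and follow-up.

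On tissue supply, footnote 3 of the Study Procedures Table reads: "Tissue collection will occur post SOC surgery and will be coordinated with the UWCCC TSB". The assay comes from patient tissue too: "Patient-derived uVESSEL models (from primary & metastatic sites".

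The one model that 3.2.2 describes in detail has a different outcome: "More specifically we will use the objective response (dichotomous endpoint of yes or no) measured using PSMA-based PET/CT as a dependent variable".

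**The concern.** A predictive claim needs an outcome that could have been changed by the treatment whose effect is being predicted. Vascular density and staining on a nephrectomy or excision specimen are settled before the first dose. If such a measure is the dependent variable, the model describes how ex vivo drug sensitivity relates to baseline tumor biology. That may be interesting, but it says nothing about whether the patient responds. Under 3.2.2 the result would nevertheless fall under an objective whose stated aim is predictive power and validation, and 10.2 groups the endpoint with measures of patient response. With 15 patients, a positive finding of this kind could easily be over-read as support for the assay.

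**Working it through.** The plan states no figure on this point, so the check traces specimens and timing.

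1. **Treatment status at surgery.** The exclusion criteria in 4.0 rule out prior systemic therapy for RCC. Section 5.0 has systemic therapy begin once the patient has recovered from surgery.
2. **When tissue is taken.** The Study Procedures Table has one tissue row with one mark, and footnote 3 ties it to standard-of-care surgery. Section 5.0 (Blood and Tissue Collection) has the Biobank supply samples from the kidney, lymph nodes and excised metastatic sites. Biopsy of metastatic sites is placed after PET1 and before PET2A, which also precedes therapy. No on-treatment or post-treatment tissue is scheduled.
3. **What the assay is made from.** Sections 3.2.1 and 5.0 draw the uVESSEL from the same surgical and Biobank collection.
4. **What can follow.**

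| Candidate outcome | Observed after therapy starts? |
|---|---|
| PSMA-PET response (PET2B at 12-16 weeks; PET3B and PET4 where done) | Yes |
| RECIST 1.1 response, tumor size change, disease control | Yes |
| Vascular density, PSMA staining, neovascularization staining | No, on the scheduled tissue |
| Circulating tumor cells | Not stated; taken from blood, times not given |

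Only the third row is affected.

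5. **Staining change over treatment.** A change needs at least two specimens per patient, one of them after therapy starts. The schedule provides one collection, before therapy, so the summary in 10.2 cannot be produced from it.

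**Illustration only.** The documents give no correlation between uVESSEL readouts and tissue staining and no significance criterion for these models. Assume that a readout U and the latent staining H share a tissue trait T:

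U = √ρ·T + √(1−ρ)·E₁ and H = √ρ·T + √(1−ρ)·E₂, so corr(U, H) = ρ.

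Cut H at −1.2, −0.4, 0.4 and 1.2 to give the 0-4 grade in 10.2. Let patient response be independent of U, with probability 0.30 (the response rate expected in 10.2). With n = 15, a two-sided Spearman test at 0.05 and 4,000 simulated trials per value:

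| Assumed ρ | Nominal association with staining grade | Nominal association with patient response |
|---|---|---|
| 0.3 | 17% | about 5% |
| 0.5 | 42% | about 5% |
| 0.7 | 80% | about 5% |
| 0.9 | 99% | about 5% |

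The last column is the false-positive rate, because response was simulated as unrelated to the assay. The table shows that a tissue-outcome model can come out positive without any relation to patient response. It does not show how often that would happen in this trial.

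**The case against.** The strongest reply is that every model the plan specifies uses a patient outcome: PSMA-PET objective response in 3.2.2; objective response, tumor size change and disease control in 10.2; PET/CT response in 3.2.3. No pathology-outcome model is written out, and 10.2 calls the analysis exploratory and warns against expecting clear discrimination. This stands as a limit on scope, because the lead analyses are unaffected. It does not remove the point. The detailed model in 3.2.2 elaborates the general sentence without withdrawing it, and 10.2 repeats pathology as a dependent variable.

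A second reply is that 10.2 intends pathology to be longitudinal and speaks of confirming imaging findings pathologically. The intention is there, but no scheduled specimen can deliver it. In the extracted table the tissue mark sits in the column for visits before and during first systemic therapy, but its footnote places collection at surgery.

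Three stronger readings are tempting, and the documents do not support them:

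- **Predictor and outcome are two readings of one untreated specimen.** The predictor is the uVESSEL's response to drug: 10.2 has control plus four agents, three dose levels and four repeated measures. PSMA appears on both sides, as a uVESSEL readout and as a stain, but PSMA expression under drug is not the same quantity as baseline staining. The documents show a shared collection; they do not show that the same block is stained and cultured.
- **All pathological endpoints are compromised.** Circulating tumor cells come from blood at unstated times, so deleting the word pathological outright would discard a possibly valid outcome.
- **A misleading positive is likely.** That depends on correlations nobody has stated, and at the low end of the range shown it is uncommon.

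**Conclusion.** The point holds in a limited form. Tissue vascular density, PSMA staining and neovascularization staining, as scheduled, precede all systemic therapy and cannot serve as outcomes in a model said to predict response to it. An association between uVESSEL drug response and these measures would not be evidence of predictive power. The planned summary of staining change conflicts with the tissue schedule.

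A reader might infer that the validation objective as a whole fails. It does not, because the imaging and clinical outcome models are untouched. The conclusion rests on the stated order of surgery, tissue collection and therapy, and on the absence of any scheduled later tissue. It does not depend on the simulation, whose correlations are assumed. The change is worth making because it alters what the trial may claim.

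**What to change.** 1. In 3.2.2 and 10.2, limit the dependent variables of the predictive models to outcomes observed after therapy starts: PSMA-PET response, RECIST 1.1 response, tumor size change and disease control. Include circulating tumor cells only if the blood is drawn after therapy starts, and state when it is drawn.
2. Report the association of uVESSEL readouts with baseline tissue pathology separately, as assay characterisation, and do not count it toward predictive power. Baseline pathology could instead enter as a covariate, but at the expected 30% response rate 15 × 0.30 = 4.5 responders leaves little room for one in a logistic model, so separate reporting is the more practical choice.
3. In 10.2, move tissue pathology out of the sentence on measures of patient response. Reconcile the staining-change summary with the Study Procedures Table by removing it, or by limiting it to patients in whom later tissue happens to be obtained in standard care.

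The cost is wording in two sections and no new data. The downside is that fewer models can be reported as predictive.

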3.2.3 Evaluate the predictive power and validate in-vitro immune therapy models

At the moment we are expanding our uVESSEL patient-specific organotypic models (Fig. 2) to contain more cell types from the tumor microenvironment (cancer epithelial, endothelial, immune, stromal) in similar proportions as found *in vivo*.

Patient tissue can be disaggregated, specific cell types isolated and placed in the uVESSEL model (Bischel 2014) (Jimenez-Torres et al 2019). Tumor spheroids can be created from a mixture of tumor epithelial cells and immune cells, to mimic tumor-infiltrating leukocytes, embedded in a hydrogel matrix (Sung 2014). Tumor spheroids model solid tumors and replicate the hypoxia and

[figure not shown]

Fig. 2. A) Left: model scheme showing a tumor spheroid flanked by 2 endothelial lumens. Right: a 4-microdevice array. Confocal images of B) a tumor spheroid (blue) and immune cells (green). C) tumor organoid (green) with hypoxic core (red). D) lateral endothelial lumen.

nutrient starvation observed *in vivo* in RCC (Fig. 2). Hypoxia influences the microenvironment by significantly suppressing the anti-tumor response by increasing regulatory and immunosuppressive immune cell phenotypes and reducing cytotoxic lymphocyte functions (Noman 2015). Likewise, the uVESSEL model allows for the creation of lumen structures within a hydrogel matrix that can be lined with endothelial cells to form microvessel structures, mimicking the highly vascularized nature of RCC (Jimenez-Torres 2019). Thus, we can create a carefully controlled model tumor microenvironment made entirely of primary cells all from the same patient (Fig. 2) that can be treated with various immune checkpoint inhibitors, TKI's or combinations thereof with readouts examining tumor growth, immune cell phenotype and function and angiogenesis. Our functional endpoints include spheroid size variation/viability, as well as the angiogenic sprouting endpoint already developed for TKI predictive value. Both outputs can be expressed as a dichotomous endpoint of responders/non-responders for the validation of uVESSEL performance with patient response as observed in PET/CT.

4.0 RESEARCH DESIGN AND METHODS:

Study Design: This study is designed as a single cohort study without randomization or stratification.

Study population: A total of 15 patients diagnosed with clear cell RCC will be enrolled in this study. Achieving the objectives outlined above will require the collection of tissue from the UWCCC Biobank, the review of subject medical records, and subject participation in up to four research visits lasting approximately 2 – 3 hours.

Inclusion Criteria:

- Patients diagnosed with locally advanced (\geq cT3) or metastatic clear cell RCC, as proven by biopsy.
- Adults, 18 years of age or older.
- Surgical candidates who have clinical indication for nephrectomy and standard-of-care biopsy of metastatic disease followed by possible standard of care systemic anti-angiogenesis based treatment regimen
- Have consented to participate in the UWCCC Biobank.

Exclusion Criteria

- Patients who have received prior RCC systemic therapies
- Prior history of prostate cancer
- Prior history of any other malignancy within the last 2 years, other than skin basal cell or cutaneous superficial squamous cell carcinoma that has not metastasized and superficial bladder cancer
- Unable to lie flat during or tolerate PET/CT
- Serum creatinine > 2 times the upper limit of normal

Subject identification and recruitment

GU Oncology staff will identify patients who meet the eligibility criteria and will introduce them to this research opportunity. Those interested will be referred to a study team member who will review the purpose of the research as well as details about participation.

Informed Consent and Subject Information

The consent process will occur prior to the administration of research PET/CT procedures. Potential subjects will meet with a study team member to review the information in the consent form including study procedures, risks associated with participation, alternatives to participation and whom to contact for additional information. Any questions will be addressed prior to the start of any study procedures and all subjects will be reminded that participation is optional and they can change their mind at any time.

The consent process will occur prior to the administration of research procedures. During the COVID-19 pandemic, consent procedures will be conducted by phone, when possible, to minimize face-to-face contact subjects have with the research team. A copy of the consent form will be mailed or emailed to subjects prior to the scheduled consent phone call. If emailed, the consent form will be encrypted. A study team member will call potential subjects at the scheduled time to review the information in the consent form including study procedures, risks associated with participation, alternatives to participation and whom to contact for additional information. Any questions will be addressed during the course of the phone call and subjects will be encouraged to contact the study team with any questions or concerns

they might have at any time. Upon completion of the consent process, a copy of the signed consent form will be provided in one of the following ways depending on each subject preferences and capabilities:

- Electronic signature will be provided using DocuSign
- Subject will be asked to scan a copy of the entire consent document and email it back to the study team.
- Subject will be asked to take a photo of the signature page and email a copy to the study team.
- If subjects are unable to provide an electronic copy of the signed consent form, they will be asked to bring a copy of the form to the research visit.

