10.0 STATISTICAL CONSIDERATIONS

As noted in section 3.0, the primary objective is to evaluate response to anti-angiogenesis therapy using PSMA-based PET. Other endpoints such as qualitative objective response based on RECIST 1.1 and quantitative CT-based tumor size and SUV parameters will also be evaluated. The secondary objectives are 1) to measure therapy response of patient-derived uVESSEL models using multiple endpoints such as vessel sprouting, PSMA expression and cell death and 2) to evaluate the predictive power and validate the uVESSEL model for clinical outcomes.

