10.1 Sample size justification

A total of 15 patients will be recruited into this clinical study. This is based on the feasibility and availability of suitable patients over the funding period with approximately five patients per year. With 15 patients, the width of a 95% confidence interval for the probability of qualitative response based on PSMA-PET and objective response based on RECIST 1.1 will be less than 0.253 and the mean of quantitative endpoints such as CT-based tumor size and SUV parameters will have standard error that is 0.258 times the sample standard deviation.

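### The uVESSEL-to-PET validation model reduces PSMA-PET response to yes/no, and section 3.2.3 lets the assay be cut too; no analysis relates continuous SUV change to the continuous assay effect

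*Combined protocol and SAP*

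**What the plan says.** Section 3.2.2 specifies the validation model, with "objective response (dichotomous endpoint of yes or no) measured using PSMA-based PET/CT as a dependent variable in a logistic regression model". Section 10.2 repeats it: "we will use the objective response as a dichotomous endpoint as a dependent variable in a logistic regression model". The predictor there is again the uVESSEL response. Section 10.2 does not say which imaging method defines the response there; 3.2.2 does.

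Section 3.2.3, on the immune-therapy models, describes the assay side: "Our functional endpoints include spheroid size variation/viability, as well as the angiogenic sprouting endpoint already developed for TKI predictive value". It continues: "Both outputs can be expressed as a dichotomous endpoint of responders/non-responders for the validation of uVESSEL performance with patient response as observed in PET/CT". Section 10 lists only the first two secondary objectives, so this is all the analysis text that 3.2.3 has.

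On the PET side, section 10.0 says that "quantitative CT-based tumor size and SUV parameters will also be evaluated", and 10.2 plans longitudinal mixed models for the PET measures. For predictive modelling, 10.2 adds continuous tumor size change, disease control (yes/no) and, as an alternative, clustering. It also explains that metastases can respond to anti-angiogenic drugs with little change in size, which is why PSMA-PET is used.

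**The concern.** The study measures PET uptake on a continuous scale, and the assay readouts can be analysed without a cut. The analysis meant to link the two nevertheless turns PET into a yes/no variable, and 3.2.3 allows the same for the assay. Continuous tumor size change does not fill the gap, because the plan's own argument is that size is the less sensitive measure of this drug effect. Clustering sorts patients into groups and does not estimate an assay-to-SUV association.

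With the sample size fixed by feasibility, the scale of analysis is something the sponsor can still choose. A real association between assay and PET could be missed because of the cut. In addition, no threshold is stated for PET response or for the assay, so each cut can be placed after the data are seen.

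**Working it through.** **Inputs from the plan.** Section 10.1: "A total of 15 patients will be recruited into this clinical study". Section 10.2: an expected objective response rate of around 30% on pazopanib or sunitinib.

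**Assumed, because the documents give no value.** 30% responders on PSMA-PET and on the assay; bivariate normal assay effect and SUV change; true correlation 0.5 to 0.8; 15 complete pairs; two-sided 5% tests.

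**The plan's own figures.** It states none for this validation. Its general precision figures are a standard error factor of 0.258 and a 95% interval width that "will be less than 0.253 and the mean of quantitative endpoints such as CT-based tumor size and SUV parameters" have at n=15. The first reproduces: 1/√15 = 0.258. The second is a half-width: 1.96 × √(0.25/15) = 0.253, so the full width is 2 × 0.253 = 0.506. That is a separate matter and does not enter below.

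**Information kept after a cut.** For a normal variable cut so that a share p are responders, the fraction kept (near zero correlation) is φ(z)²/[p(1−p)], where z is the normal quantile at 1−p and φ the normal density. If both variables are cut, the two fractions multiply.

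- One cut, p = 0.30: z = 0.524, φ(z) = 0.348, so 0.1209/0.21 = 0.576. Effective n = 15 × 0.576 = 8.6.
- One cut, p = 0.50: 0.637, effective n 9.5. One cut, p = 0.20: 0.490, effective n 7.3.
- Both cut at 0.30: 0.576² = 0.331, effective n 5.0. Both at 0.50: 0.405. Both at 0.20: 0.240.

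Cutting PET alone therefore loses 36 to 51% (42% at 30% responders). Cutting both loses 59 to 76% (67% at 30%).

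**Power by simulation** (20,000 trials per correlation, n=15, cuts at 30% responders):

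| True correlation | Both continuous, Spearman | PET cut only, exact Mann-Whitney | Both cut, Fisher exact | Both cut, phi t test |
|---|---|---|---|---|
| 0.5 | 44% | 25% | 14% | 26% |
| 0.6 | 62% | 37% | 21% | 36% |
| 0.7 | 81% | 51% | 31% | 48% |
| 0.8 | 94% | 69% | 46% | 65% |

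Rejection rates at zero correlation are 5.2% (Spearman), 4.0% (Mann-Whitney), 1.7% (Fisher) and 4.6% (phi t test). Fisher's test is thus well below its nominal level, and the phi t test is the fairer measure of what the double cut costs.

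**Events for the logistic model.** At 30%, 15 × 0.30 = 4.5 responders are expected. The chance of two or fewer is 0.7¹⁵ + 15(0.3)(0.7¹⁴) + 105(0.3²)(0.7¹³) = 0.005 + 0.031 + 0.092 = 0.127, about 13%.

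**The case against.** A reader might infer from 3.2.3 that the plan cuts both assay and PET throughout, and so discards most of the information. The text does not support that. The two outputs in that sentence are both assay readouts (spheroid size or viability, and sprouting), and the wording permits a cut without requiring it. In 3.2.2 and 10.2 the uVESSEL response enters as a predictor with no prior threshold stated; the two groups in 3.2.2 are what the model produces. For that model only the PET side is cut, and more than half of the information survives at 30% responders. A reader might also infer that this is the costliest analysis choice in the plan. No other choice has been measured against it, and the plan has others, such as pooling patients on different drugs.

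The sponsor can add that 10.2 declares the analysis exploratory and concedes that clear discrimination cannot be expected at n=15, so power at 5% is not its criterion. Section 10.2 also admits imaging endpoints in general as dependent variables, which could include SUV. PET is read on a three-point scale as well, so continuity applies only to the SUV parameters.

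These points narrow the concern without removing it. The model that 10.2 goes on to specify has a binary outcome, and no passage names SUV change as the outcome against the assay. An exploratory study of 15 patients is better served by an estimate with an interval than by a classification. A continuous analysis does bring choices of its own (readout, dose, SUV metric, lesions, scan pair), so it helps only if these are fixed in advance.

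**Conclusion.** The concern holds on the PET side of the specified model and, as a permitted option, on the assay side in 3.2.3. Cutting PET alone costs about 42% of the information at 30% responders and lowers power by 19 to 30 points across correlations 0.5 to 0.8 (for example, 81% to 51% at 0.7). If the assay is cut as well, about two thirds is lost, and power at 0.7 falls to 31% by Fisher or 48% by the phi t test.

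These sizes rest on normality, on an assumed 30% share for PET and assay (the plan's 30% is an objective response rate), and on 15 complete pairs. Section 5.0 gives locally advanced patients no PET2A until metastatic disease is found, so pairs may be fewer, which would lower every power figure. The change is worth making, but nothing here makes the study invalid.

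**What to change.** In 3.2.2 and 10.2, make the lead assay-to-PET analysis the rank correlation, with 95% confidence interval and scatter plot, between each patient's continuous uVESSEL inhibition and percent change in PSMA-PET SUV. Name in advance:

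- one assay readout, the assay drug matched to the patient's therapy, the assay dose level and the tissue source;
- one SUV metric and one lesion rule;
- the scan pair that spans the anti-angiogenic therapy (PET2A/PET2B or PET3A/PET3B).

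Keep the logistic, responder/non-responder and clustering analyses as supportive, and report the number of complete pairs. The cost is SAP wording only: no new scans, samples or patients.
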